## 2. HOSPITAL PROVIDER TRAINING

*“People who inject drugs are afraid that when they come into hospital they will be “ignored” and will have to wait for some time before they receive OST. This leads them to “tank up” before coming into hospital - which only serves to reinforce the often negative view that staff have of this vulnerable patient group”. (Infectious Disease Consultant, St James's University Hospital, Leeds)*

Our consultations with healthcare professionals align with the international literature: PWUO are perceived as a challenging population to manage in the hospital setting. Limited training or skills in working with substance dependent patients can exacerbate tensions and workplace stress. There is a clear need for a dedicated training package that can support development of de-escalation strategies and improve patient-centred care and communication as well as provide education on the specifics of OST dosing and management. We have two specialist addiction pharmacists in our team (JS, RG). JS will lead training development, in collaboration with Exchange Supplies who will host it on their training site. This will be a similar format to their NICE accredited Needle and Syringe Provision training (developed with JS) (Figure 4).

iHOST training will be offered to healthcare professionals and administrative staff in: A&E, Medical Assessment Unit, ITU/HDU, medical and surgical and all Pharmacy staff. The training will be compulsory for the iHOST champions; voluntary for all other inpatient and pharmacy staff. We have sought leadership support by engaging with relevant medical consultants, chief pharmacists and senior leadership teams, which we will continue to engage with during the optimisation phase, to enable maximum participation.

[figure not shown]

Figure 4. NSP Practitioner Training  
[https://training.exchangesupplies.org/nsp\\_training](https://training.exchangesupplies.org/nsp_training)

Our module will follow the NSSCT e-learning format, which includes a mandatory pre- and post-assessment measure of knowledge and attitudes drawing on validated questionnaires. We will monitor how long people are logged on and the percentage rate of completion, with content modifications for dissemination (P4) on basis of usage statistics, assessment measures and qualitative interviews.

The training will be designed to reduce stigma and develop confidence in communications and de-escalation strategies. For healthcare staff, it will also aim to improve understanding of the basic therapeutics and key safety around prescribing and administering OST, using DHSC/PHE guidelines as core underpinning evidence. It will cover key points in induction, titration and discharge planning of people in receipt of OST. There will be an additional section for the iHOST champions, explaining their role and how to deliver it to maximise effect. It will take no longer than 1 hour to complete for clinical staff, up to 20 minutes for non-clinical staff.

### 3. ADVOCACY HELPLINE

[Release](#) has been providing advocacy and legal support to people who use drugs for over 50 years. The organisation set up a specialised helpline in the early 2000s to support people with their opioid use, to help them access OST if that is what they wanted, and to ensure that the treatment they received met clinical standards. The helpline is operated by a specialist nurse advocate and is supported by volunteers - many of whom have lived experience. At the core of the service is ensuring that those who access support are treated with respect and dignity, that they are listened to, and that their rights are realised.

The hospital helpline, advertised on the 'My Meds' card, would work in a similar way to the advocacy work Release currently does. The helpline would operate between 10am and 6pm (with potential for extension dependent on demand). The helpline number can be texted to organise a call back in operating hours. Details would be taken and Release staff would contact the relevant medical team and hospital pharmacist involved in the patients care, as well as liaising with the community drug services responsible for the patient's prescription. A specific, established contact at each of the participating hospitals will be contacted in the first instance when an issue about OST access arises. Release staff would determine the local policy and whether or not there was a drug liaison service available to refer to. The aim would be to ensure that patients were supported to secure their community OST or be assessed and titrated while an inpatient as quickly as possible, and in line with current clinical guidance [71]. Release will collect data on people accessing the service including demographics, relevant hospital trust, and outcomes. This (anonymised) data will be shared with the team as part of the project evaluation on a monthly basis, or as required.

### 4. POLICY TEMPLATE

We recognize that supportive structures and policies need to be in place in order for healthcare providers to deliver culturally safe hospital care. In collaboration with our advisory group and hospital provider stakeholders we will develop a 'best practice' substance dependence management policy template. This will be optimised in phase 1, tested in phase 2 and refined iteratively throughout the project for finalisation in phase 4. This template will be informed by our NHS Trust substance dependence policy review, through which we have identified models of best practice, including in relation to use of inclusive, non-stigmatising language. It will be clinically based on the current UK Clinical Guidelines [71]. The Specialist Pharmacy Service support this approach, and we will work with them to publicise and disseminate the policy template.

### 5. IHOST CHAMPION

Champions, defined as "individual(s) who dedicate themselves to supporting, marketing, and driving through an implementation, overcoming indifference or resistance that the intervention may provoke in an organization"[72], will support the implementation of iHOST. This role will be developed with input from key stakeholders during the optimisation and feasibility phases. A role description with responsibilities and clear lines of accountability will be developed. We expect that in each hospital there will be a number of champions, reflecting different clinical roles and wards (e.g. nursing, pharmacy, A&E, ITU etc), who will support their colleagues with implementing the intervention and sustaining this. iHOST champions will be identified by asking relevant teams for volunteers to take on this role. They will receive additional training via the online course (see above). They will take on the role of encouraging the adoption of the intervention, supporting new and existing colleagues to incorporate the intervention into their practice and be a practical source of local information e.g. signpost to community drug teams and local pharmacies.

## Delivery plan

### PHASE 1 (MONTHS 1-8): IHOST OPTIMISATION

Systematic optimisation of iHOST will be carried out in collaboration with UCLH, linked drug treatment service providers and PWUO service users. Methods comprise workshops, consultations, evidence review.

#### Output 1: Optimised TOOLKIT

- a. MYMEDS card. (Lead M.H, A.N). METHOD: Workshops (n=2). SITES: Margarete Centre DTS, Better Lives DTS. PARTICIPANTS: ~7 PWUO & 3 providers per workshop (n=~20). AIM: finalise information fields, advocacy message and design. CONSULT: PPI advisory group; Exchange Supplies and Drug Treatment providers (NHS Camden & Islington; CGL, Turning Point, Better Lives) to finalise content & design.
- b. Training modules (lead J.S, A.P). METHOD: Workshop (n=1) SITE: UCLH. PARTICIPANTS: UCLH A&E, acute admissions, high burden wards, drug liaison; hospital pharmacy staff (n=~10). AIM: Assess local need, workshop content. CONSULT: Key stakeholders (UCLH education team; NHSEI, HEE, PHE OST leads, PPI group); INTEGRATE: emerging evidence review and cultural safety workshop findings.
- c. Advocacy helpline (lead N.E). METHOD: Workshop (n=1) SITE: Release. PARTICIPANTS: Release staff (n=4); PWUO (n=6); Hospital providers (n=4). AIM: Assess local need, workshop content.
- d. Policy template (lead JS, RG). CONSULT: Key stakeholders (PHE OST leads; SPS Lead Medication Safety Officer, Guild of Healthcare Pharmacists, PPI group ); INTEGRATE: NHS Trust policy synthesis findings.
- e. 'Local iHOST champion' (lead AS, Research nurse). SITE: UCLH; CONSULT: key UCLH staff (ward sisters, education team etc); hospital drug liaison teams from key sites where collaborative relationships between hospital and drug treatment teams are well established and/or innovative. AIM: produce role description, inform training component (see b).

#### Output 2: Evidence and systems review

- a. Systematic review (lead DL) of the published peer-review literature describing interventions for improving OST provision in acute hospital settings for people who are dependent on illicit opioids.
- b. Policy synthesis: (lead JS) Finalise NHS Hospital policy analysis, write up for peer-review publication and to inform template development.
- c. Clinical information systems review: (lead DL). Review patient records systems at UCLH, such as EPIC, to determine the feasibility of identifying patient groups and outcome measures. Refine analysis plan if necessary. Consult leadership within the local integrated care system to understand key strategic opportunities for implementation across the health and social care system.

#### Output 3: Patient involvement set up (lead MH, AN)

**PPI workshop #1:** Introduce study. Review all PWUO materials for acceptability. Introduce and invite feedback on cultural safety concept and logic model. Explore training or other research support needs. Agree approach and feedback mechanisms for PPI workshops and cultural safety concept mapping over project.

### PHASE 2 (MONTHS 9-14): FEASIBILITY TESTING

We will introduce iHOST components to UCLH and linked drug treatment services and assess the feasibility of their practical application and evaluation measures. Findings will be disseminated to PWUO and providers, who, with the advisory board, will advise of pragmatic adjustments to be made to iHOST components and/or evaluation measures before implementing for evaluation (phase 3).

#### Output 1: Embed and test iHOST toolkit (Lead MH, AN)

- a. Conduct non-participant observations of 'iHOST champion' interactions with UCLH staff to assess the acceptability and impact of methods to sensitise staff to the iHOST concept and toolkit. (n=~8 sessions).
- b. Present iHOST concept to staff at local drug treatment services (staff meetings), provide MY Meds cards for distribution to their clients and order/delivery links for restocking.
- c. Conduct non-participant observations of My Meds card provision in DTS and use at UCLH (where feasible) to assess acceptability and iHOST implementation fidelity (n=~16 sessions).

- d. Conduct in-depth interviews with 6 inpatient PWUO, 6 community based PWUO, 4 hospital staff, 4 drug treatment staff (n=20 total) to explore iHOST acceptability, impact on practice, contextual barriers and facilitators to implementation.

#### Output 2: Evaluate feasibility of outcome measures at UCLH (lead DL, JS)

- a. Compare detailed outcomes at UCLH before and after implementation of iHOST. These include process-related measures such as time from admission to provision of OST, and outcome-related measures such as the risk of DAMA.
- b. Conduct a controlled analysis of changes in two outcomes (DAMA and 28-day readmission) between UCLH and other hospitals across England, using HES.
- c. Assess inbuilt staff training module evaluation measures for training impact on knowledge/attitude, acceptability and reach.

#### Output 3: Prepare for phase 3 implementation and evaluation (lead MH, DL, RG)

- a. Conduct 2 London workshops (Margarete Centre, Better Lives) with 8 providers & 12 PWUO (n=20): discuss findings, assess and collaboratively refine intervention components. Consult: PPI group meeting.
- b. Review clinical information systems at the hospital sites, refine analysis plans if necessary.
- c. Conduct 4 focus groups: 1 each at STARS (Staffordshire Humankind) and Forward Leeds (Leeds Humankind) services (14 PWUO & 6 providers, n=20), one at each hospital site (drug treatment liaison team & affiliated staff, n=16) to explore local context (current practice, perceived need), iHOST expectations and perceived quality of collaborative relationships between drug treatment and hospital services.

### PHASE 3 (MONTHS 15-28): EVALUATION

We will introduce iHOST to the Staffordshire and Leeds sites, where it will be embedded for 3 months prior to evaluation. The lead clinician and iHOST 'champion' will coordinate set up, staff sensitisation and training promotion. UCLH will continue to implement iHOST.

Our methods are informed by the MRC guidance for evaluating complex interventions [73, 74] and will assess fidelity, quality and acceptability, clarify causal mechanisms, and identify contextual factors that may be associated with success. We will use mixed data collection methods including a quantitative measurement of outcomes based on analysis of routinely captured data, qualitative analysis of staff and patient perceptions of the programme, and reporting of the programme structure including patient volumes and costs of implementation. In-depth fieldwork will be carried out at each site to explore how iHOST 'works' (or does not work) from the perspective of PWUO, hospital staff and drug treatment providers [11].

#### Output 1: Quantitative evaluation (lead DL, VH, AM)

- a. Compare detailed outcomes including those not available in HES such as OST prescription rates, time from admission to OST initiation, at Leeds and Staffordshire hospitals before and after iHOST.
- b. Conduct a controlled analysis of changes in two outcomes available across all HES data (DAMA, 28 day emergency readmission) comparing those with HES codes identifying PWUO in Leeds and Staffordshire hospitals with other hospitals across England, using HES.
- c. Assess the acceptability, reach and perceived impacts of staff training activities through self-complete survey data embedded into the training platform (n~150 staff).
- d. Assess, from dedicated drug treatment service records, MY Meds card uptake among service users.
- e. Undertake a cost-effectiveness / cost-consequences analysis of iHOST compared to not providing it.

#### Output 2: Qualitative process evaluation (Lead MH)

- a. Conduct interviews with 8 PWUO and 6 providers at 4 sites (n=32 PWUO; 24 providers): the 2 intervention hospitals and 2 linked drug treatment services. Interviews to explore: iHOST acceptability, perceived impact on practice, barriers and facilitators to implementation and uptake, contextual and

- un/anticipated mechanisms of change, additional needs/concerns (ie, discharge planning; other barriers/facilitators to timely presentation, treatment completion and retention in community OST care)
- b. Conduct non-participant observations of iHOST delivery at each site and linked DTS (n=~30) to assess iHOST fidelity, quality, local social and contextual factors shaping iHOST implementation and uptake. Observations will be informed by a tool, developed in phase 1, with categories informed by CFIR constructs (intervention, inner and outer setting, individuals involved and process [75]) to enable quick notation of, for example, types and frequency of patient provider interactions, management and recording of DAMA, to also be expanded on in observational field notes.
  - c. Integrate analysis from Phases 1-3 to refine cultural safety framework with PPI input.

## PHASE 4 (MONTHS 29-36) PROTOCOL DEVELOPMENT AND DISSEMINATION

### Output 1: Finalise iHOST toolkit (Lead MH, AN)

- a. Conduct co-production workshops at each site (n=3, London, Stafford, Leeds) to disseminate findings, consolidate lessons, co-produce & finalise outputs with 18 PWUO & 12 providers (n=30); then PPI review and meeting.
- b. In collaboration with Exchange Supplies and Advisory Board finalise protocols and/or hard copies of card, helpline, policy template and training module for dissemination.
- c. Develop implementation toolkit for dissemination of iHOST to other NHS trusts.
- d. Develop and deliver online live webinar training and slide-sets to accompany the toolkit targeted at commissioners, drug treatment providers, hospital consultants, A&E, pharmacy and high burden wards.

### Output 2: Multi-disciplinary dissemination and policy advocacy (Lead NE, MH, JS)

- a. Produce a policy-orientated health service delivery report
- b. Open access peer-review publications, community publications/presentations.
- c. Targeted presentations & meetings with: Public Health England; National Drug Treatment Providers; Specialist Pharmacy Service; NHS England, Royal College of General Practitioners; ICS commissioners.
- d. Resource designed by Linnell publications specifically for PWUO to raise iHOST awareness:

## Analysis

### QUANTITATIVE EVALUATION

Our quantitative analysis of outcomes has two elements: (1) a detailed analysis of OST provision and patient outcomes before and after implementation of iHOST, using data extracted from local clinical systems at iHOST hospitals (i.e. an uncontrolled analysis) and covering all quantitative outcomes and (2) a controlled analysis of the two primary outcomes (DAMA and 28-day readmissions), comparing PWUO in the iHOST sites with other hospitals across England, using patient-level HES from NHS Digital. These two elements will both be implemented during the feasibility stage at UCLH and the formal evaluation at Leeds and Staffordshire hospitals. Depending on local data availability, there may be some differences in the definition of locally measured outcomes between iHOST sites.

**1. Detailed before/after analysis based on local data.** This will involve comparison of OST provision and outcomes before and after implementation of iHOST. We will derive patient-level data on each outcome and use regression to test whether there is a difference in the outcomes for patients admitted in the 12 months before the iHOST “go-live” date and those admitted in the 12 months after this date, adjusting for potential patient-level confounders such as the reason for admission. Outcomes will be grouped into: (a) patient outcomes in all those identified as PWUO; b) characteristics of OST prescribing in those receiving OST.

- a. **Patient outcomes in PWUO:** Based on phase 1 feasibility work a range of approaches will be used to identify PWUO in the participating hospitals including: free test records of OST prescriptions in the community, and diagnostic coded for opioid use those with opioid poisoning or injecting-related injuries. Outcomes will include receipt of OST during admission; DAMA; and 28-day emergency readmissions (all binary outcomes). The analysis will then use logistic regression to compare the probability of each outcome for this patient group in the 12 months before vs. the 12 months after the iHOST “go live” date.

Sensitivity analyses will use wash-out periods 3 months either side of the intervention, as there may be changes in practice in the run up to the start date and the intervention may take some time to embed.

- b. Amongst people prescribed:** People who are prescribed OST in the hospital will be identified using pharmacy records. The time between admission, prescription of OST, receipt of OST and the OST dose will be obtained from clinical records. These outcomes have been selected in discussion with iHOST partners, with delays to OST and low doses cited as problems. The base population will be all patients receiving OST. The modelling strategy will depend on the distribution of the outcomes, for example analysis of the time between admission and receipt of OST may use gamma regression.

UCLH has investigated the feasibility of collecting these data. The outcomes can be extracted from pharmacy and discharge summary records. We have identified several approaches to defining the patient group discussed in (b), including searching free-text using CogStack software, and will refine these and potentially conduct sensitivity analysis with different patient groups.

**2. Controlled analysis using HES (difference-in-difference [10]).** This analysis will involve measuring the change in primary outcomes at iHOST sites before and after iHOST implementation and comparing this change to other hospitals over the same time period. HES does not show whether patients received OST in hospital, and we will therefore need to identify a group of patients who may benefit from iHOST. Our planned inclusion criteria will be all admissions at acute hospital trusts in the 12 months before or after the iHOST “go-live” date, the patient is aged 18-64 at admission, and the patient has an ICD-10 diagnosis of opioid dependence (F11) in any diagnostic position, either in that admission or an admission at any hospital nationally in the previous 12 months. For each admission we will derive the two primary outcomes: DAMA and 28-day emergency readmission. We have previously used HES to measure these outcomes in comparable populations [32, 76] and are familiar with the structure of HES. We will then fit logistic regression models where the dependent variable is the outcome and the independent variables include an interaction term between the iHOST site status and whether the patient was admitted before or after iHOST implementation. We will also include patient-level confounding variables such as age, comorbidities, and the primary reason for admission, and a random intercept for the hospital site. This analysis addresses the question “did the risk of self-discharge/readmission reduce more at iHOST sites than at other hospitals”? Depending on the number of patients with admissions at the same hospital both before and after iHOST “go-live”, or at similar dates at iHOST sites and other hospitals, it may also be possible to conduct a sub-analysis of within-patient differences using conditional regression.

**3. Cost-effectiveness (CEA) / cost-consequences analysis (CQA).** We will perform a CEA and CQA of the iHOST intervention compared to not using it, using the results from sections 1 and 2 above. Both analyses will use an NHS cost perspective and include the cost of iHOST implementation and the costs of hospital visits. The CEA will be expressed in terms of the additional cost to prevent an episode of DAMA within 28-days of discharge. The CQA will present results in a tabular manner and will additionally include outcomes such as the time to OST prescription. We are proposing to use the simpler approach, rather than undertake a more usual cost-utility analysis, because of the limited opportunity to collect data on health outcomes, and the importance of considering non-health outcomes such as measures of OST prescription. Moreover, given that iHOST is likely to be relatively inexpensive to implement, and the difficulty of linking outcomes such as DAMA to future health events, we will restrict the analysis time horizon to the study period; no decision modelling is planned. Appropriate sensitivity analysis will be undertaken.

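### Adjoining 12-month windows around an undefined go-live date put the 3-month embedding period inside the main comparison, and the 12-month UCLH comparison does not fit its 6-month feasibility phase

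*Protocol*

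**What the plan says.** **Embedding.** The Phase 3 section introduces iHOST at the Staffordshire and Leeds sites, "where it will be embedded for 3 months prior to evaluation". The delivery plan in the Summary of Research says the same.

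**Analysis windows.** Under Quantitative evaluation, the local before/after analysis compares the "12 months before vs. the 12 months after the iHOST" go-live date. The controlled HES analysis of the two primary outcomes takes "all admissions at acute hospital trusts in the 12 months before or after the iHOST" go-live date. Neither leaves a gap. Neither says whether go-live is the day iHOST is introduced or the day embedding ends.

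**Wash-out.** "Sensitivity analyses will use wash-out periods 3 months either side of the intervention". The stated reason is that practice may change ahead of the start and that iHOST may need time to bed in. This stands under the local analysis. The HES paragraph has no counterpart.

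**UCLH.** Of the local and HES analyses the protocol says: "These two elements will both be implemented during the feasibility stage at UCLH and the formal evaluation at Leeds and Staffordshire hospitals". The feasibility stage is headed "PHASE 2 (MONTHS 9-14): FEASIBILITY TESTING". Its opening paragraph has the findings feed into adjustments of the intervention or the evaluation measures before Phase 3.

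**Calendar.** The Phase 3 heading reads "PHASE 3 (MONTHS 15-28): EVALUATION", while the Summary delivery plan and the opening of section 5 give months 15-29. The Project timeline (section 7) marks clinical and HES extraction only from the months 16-18 block to the months 28-30 block.

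**The concern.** One part of the protocol treats the embedding months as preceding evaluation, while the analysis section has no place for them outside the comparison. Two adjoining 12-month windows that meet at go-live must absorb those three months on one side or the other.

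- If go-live is the introduction, a period in which iHOST may not yet be working is analysed as fully exposed.
- If go-live is the end of embedding, a period in which iHOST is already running is analysed as unexposed.

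Where the effect is partial in those months, both choices pull the estimate toward no effect, by different amounts. The go-live date also remains open, so the contrast being estimated is not fixed in advance. Settling it after outcome data are seen would allow the primary result to move.

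At UCLH the issue is timing. A comparison needing twelve months after go-live is placed in a six-month phase whose purpose is to inform the phase that follows.

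**Working it through.** **Inputs from the protocol**
- Target: 33% relative reduction in self-discharge, 80% power, about 250 patients per intervention site; 400-500 PWUO admitted per site per year (Sampling and Recruitment, Clinical review).
- Cited risk of leaving before treatment is complete: 25-30% (Background and Rationale). It is not stated to be the simulation input.
- Embedding 3 months; windows 12 months each.

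**Assumptions, not in the protocol**
- Two-sided alpha 0.05 and a simple comparison of two proportions, before versus after. This is not the HES difference-in-difference model.
- Even monthly admissions, so embedding is 3/12 = 0.25 of a window.

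**1. The protocol's own figure.** The baseline, and whether 250 is per period, are not given, so 250 per site cannot be reproduced uniquely. It yields 80% if 250 is per site per period, the two sites are pooled (500 v 500) and the baseline is 20%. For a single site (250 v 250) it needs a baseline of about 34.5%. At 25-30%, power is 62-73% for 250 v 250 and 90-95% for 500 v 500.

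**2. Where the embedding months fall**

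| Go-live at Leeds/Stoke | Post window | Embedding (months 15-17) counts as | 28-day follow-up runs into |
|---|---|---|---|
| Introduction, month 15 | 15-26 | first 3 post months | month 27 |
| After embedding, month 18 | 18-29 | last 3 pre months | month 30 |

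**3. Attenuation of a true 33% reduction**

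Let f be the share of the full effect present during embedding.

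In the post window, the apparent reduction is 0.33 × (0.75 + 0.25f):
- f = 0: 0.33 × 0.75 = 24.75%
- f = 0.5: 0.33 × 0.875 = 28.9%

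In the pre window, it is 1 − 0.67 / (1 − 0.33 × 0.25f):
- f = 1: 1 − 0.67/0.9175 = 27.0%
- f = 0.5: 1 − 0.67/0.95875 = 30.1%

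**4. Power at the expected volume** (two sites, 2 × 400 to 2 × 500 = 800-1000 per period)

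| Scenario | 25% baseline, 800 / 1000 | 30% baseline, 800 / 1000 |
|---|---|---|
| No dilution | 98% / 99.5% | 99.6% / 99.9% |
| Embedding in post, no effect yet | 85% / 92% | 92% / 97% |
| Embedding in post, half effect | 94% / 98% | 98% / 99% |
| Embedding in pre, full effect | 87% / 94% | 94% / 97% |
| Embedding excluded, matched 9 v 9 months | 94% / 98% | 98% / 99% |

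The half-effect row and the 9 v 9 row agree to within rounding. At that point excluding embedding buys no power; it removes the bias.

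At the smaller 500 v 500 and a 20% baseline, the undiluted 80% falls to 54% with no effect in embedding and to 68% with half effect. Matched 9 v 9 months (375 v 375) also gives 68%.

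**5. UCLH.** A month-9 go-live gives a post window of months 9-20, with 28-day readmissions into month 21. Phase 2 ends at month 14, so months 9-14, at most 6 of the 12, fall inside it. The timeline marks no extraction before the months 16-18 block.

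**6. Phase 3 end.** With go-live at month 15 and no gap, follow-up into month 27 fits both stated end months (28 and 29). A full 12-month post window starting at month 18 ends at month 29, one month past the Phase 3 heading. Its readmission follow-up, into month 30, passes both.

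**The case against.** The protocol sees the problem. It plans a wash-out of three months on each side, which covers either meaning of go-live and also removes run-up changes. Counting every admission from launch is a legitimate pragmatic contrast, and the Design section says the aim is practical programme information rather than the most robust effect estimate. Repeating a sensitivity analysis for HES is the kind of detail a SAP can carry. At UCLH the 12-month data will exist by about month 21, because iHOST continues there, and the systems reviews and interviews can inform Phase 3 without them.

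Much of this stands. The wash-out is real mitigation, and an all-months contrast could be defended if it were chosen explicitly. But the protocol also says embedding comes before evaluation, and the windows do not honour that. Which meaning of go-live applies decides what the main analysis estimates, so it should be settled in the protocol. The UCLH comparison is feasible later, but not in the stage where the protocol places it.

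A reader might infer that the study is left badly underpowered. The documents do not support this: at the volume the protocol expects and its cited 25-30% risk, simple power is about 85% or more even in the worst case. The steep losses need 250 per site per period, which is not how the protocol describes expected admissions. A reader might also infer that bias toward no effect is certain, or that the Phase 3 calendar cannot work. The bias depends on how much effect is present during embedding, which the protocol only says may be delayed. The overrun arises only if go-live, or a full 12-month post window, starts after embedding.

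**Conclusion.** The point holds as an inconsistency between the embedding period and the analysis windows. On either reading of go-live, three months that the protocol places before evaluation enter one side of the main local and HES comparisons.

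If the effect builds up over those months, a true 33% reduction would appear as about 25-29% (embedding counted as after, no to half effect) or 27-30% (counted as before, full to half effect). These sizes rest on even admissions and the assumed share of effect. The consequence is an attenuated estimate and an undefined contrast, rather than a serious loss of power at the planned volume.

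The UCLH conflict follows from the stated months alone: at most 6 of 12 post months lie within the feasibility phase, and no extraction is marked until after it ends. The 12-month results therefore cannot inform Phase 3 as intended. The difference between month 28 and month 29 is minor in itself, but matters once the post window is chosen.

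**What to change.** 1. Define go-live as the date iHOST is introduced at each site.
2. Exclude the three embedding months from the main local and HES analyses. Show the no-gap version and the existing wash-out of three months on each side as sensitivity analyses in both. The latter keeps the protection against run-up changes.
3. State one Phase 3 end month and a post window that fits it with 28-day follow-up. For introduction at month 15, a full 12-month window is months 18-29 with follow-up into month 30. A 9-month window is months 18-26 with follow-up into month 27, compared with the same calendar months before introduction (months 6-14).
4. Limit Phase 2 at UCLH to checks of data and outcome measures that need no 12-month follow-up, such as case counts, completeness of self-discharge coding, agreement of local data with HES, and baseline rates. Move the 12-month UCLH comparison to Phase 3.

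**Cost.** Mainly protocol wording. If the calendar cannot move, up to three months of post-period admissions are lost. With matched 9 v 9 months there is no power gain where embedding already delivers half the effect; the gain is less bias. The decision should be made before outcome data are seen.
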